8.7.2 Laboratory evaluations

8.7.2.1 Clinical laboratory

Haematology, blood chemistry, and urinalysis assessments will be conducted at Screening, Baseline, each visit during the treatment phase and Week 36.

The following laboratory parameters will be assessed:

- Blood chemistry
 - Sodium
 - Potassium
 - Chloride
 - Bicarbonate/CO₂
 - Blood urea nitrogen

-
- Creatinine
 - Fasting Glucose
 - Albumin
 - Alkaline phosphatase
 - AST
 - ALT
 - GGT
 - PT/INR
 - Total bilirubin
 - Total protein
 - Calcium
 - Lipid panel (total cholesterol, LDL, HDL, triglycerides)
 - PSA
 - eGFR (calculated based on Cockcroft-Gault formula)
 - eGFR (derived from 4-v MDRD)
 - Haematology
 - Red Blood Cell Count [RBC]
 - White Blood Cell Count [WBC]
 - Neutrophils
 - Lymphocytes
 - Monocytes
 - Eosinophils
 - Basophils
 - Haemoglobin
 - Haematocrit
 - Platelets
 - Urinalysis
 - Specific gravity
 - pH
 - Protein
 - Bilirubin
 - Glucose
 - Blood
 - Ketones
 - Leukocytes

For the purposes of summarisation in both the tables and listings, all clinical laboratory data will be reported in Standard International (SI) units.

If a lab value is reported using a nonnumeric qualifier e.g., less than (<) a certain value, or greater than (>) a certain value, the given numeric value will be used in the summary statistics, ignoring the nonnumeric qualifier.

Descriptive statistics will be presented for quantitative clinical laboratory parameters for each treatment regimen and time-point. Similarly, changes from baseline (and changes from screening for selected renal parameters; creatinine, urea, and glomerular filtration rate) will be summarised.

The change from baseline in each renal parameter to Week 24 will also be analysed via MMRM in the same manner as the change from baseline in total testosterone (see Section 8.6.3.1).

Values outside the normal range will be categorised as H (above the normal range) or L (below the normal range) based on the laboratory's reference range and these will be flagged in the individual data listings along with the Investigator's assessment.

In addition boxplots of observed values by treatment and visit will be generated for the below lab parameters:

- Hematocrit
- Hemoglobin
- Creatinine
- PSA

Qualitative urinalysis parameters (e.g protein, glucose and blood) will only be listed.

8.7.2.2 Specialised Chemistry

The following laboratory parameters will be measured at Screening and will be only be listed:

Morning cortisol
thyroid stimulating hormone (TSH)
free thyroxine (FT4)
Prolactin
25-hydroxy vitamin D
Fasting transferrin saturation

8.7.2.3 Liver Function

The number and proportion of subjects with laboratory values for liver function and enzymes of clinical concern as follows will be presented descriptively by treatment regimen:

Parameter	Level for clinical concern
ALT	> 1.5 times the upper limit of the normal range (ULN) > 2xULN > 3xULN > 5xULN > 10xULN
AST	> 1.5xULN > 2xULN > 3xULN > 5xULN > 10xULN
Bilirubin Total	> 2xULN > 3xULN
ALT/AST and Bilirubin Total	ALT/AST > 3xULN and Bilirubin Total > 2xULN (assessments to occur at the same visit)

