- 20. History of osteoporosis or fragility fractures or bone density below the expected range for age (for men < 50 years old (Z score \leq -2) based on The International Society for Clinical Densitometry definition
- 21. DEXA scan T-Score less than -2.0 at Screening or within 6 months prior to first Screening Visit
- 22. Significant acute and chronic renal or hepatic dysfunction or disease or infection (as determined by the investigator), including chronic active hepatitis B and C, or human immunodeficiency virus positivity
- 23. Significant illness within the 2 weeks prior to the initial dose of study drug that could suppress pituitary gonadal axis and decrease testosterone levels (as determined by the investigator)
- 24. Untreated sleep apnoea
- 25. Any of the following laboratory parameters at Screening:
 - Haematocrit above 50%
 - Abnormal prolactin (outside of reference range)
 - Abnormal TSH or free thyroxine (FT4) (outside of reference range)
 - Morning cortisol \leq 5 mcg/dL
 - Fasting transferrin saturation > 50%
 - Aspartate aminotransferase (AST) or alanine aminotransferase (ALT) > 3 times the ULN or bilirubin \geq 2 times the ULN (unless caused by Gilbert syndrome)
 - Estimated glomerular filtration rate (eGFR) < 60 mL/min (calculated using the Cockcroft-Gault formula)
- 26. History of cancer within last 5 years, with the exception of well treated basal cell or squamous cell carcinoma of the skin
- 27. Any history of breast cancer
- 28. Alcohol and/or drug abuse within the 12 months prior to the first Screening Visit
- 29. Current/previously reported allergy to the study drug or the class of drug under investigation
- 30. Documented history of significant psychiatric or medical disorder that would prevent the subject complying with the requirements of the protocol or would make it unsafe for the subject to participate in the study as per investigator judgment.

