Appendix II: Symptoms and Signs Suggestive of Androgen Deficiency

The following list is symptoms and signs that are suggestive of androgen deficiency:

- Reduced sexual desire (libido) and sexual activity
- Decreased spontaneous erections
- Reduced intensity of orgasm
- Gynecomastia
- Loss of body (axillary and pubic) hair (can be measured by reduced shaving)frequency
- Very small (especially ≤ 5 ml) or shrinking testes
- Infertility or documented oligospermia or azoospermia
- Hot flushes
- Decreased energy, motivation, initiative, and self-confidence
- Feeling depressed
- Mood swings
- Poor concentration and memory
- Sleep disturbance, increased sleepiness
- Mild anemia (normochromic, normocytic, in the female range)
- Reduced muscle bulk and strength
- Increased body fat, body mass index
- Diminished physical or work performance

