8.6.4.2 Change in Body composition

Descriptive summary tables will be presented for Body Weight, BMI, Waist Measurement, Hip Measurement and Waist to Hip Ratio values and change from baseline values by treatment regimen and visit.

The change from baseline in each parameter up to Week 24 will be analysed via MMRM in the same manner as the change from baseline in total testosterone (see Section 8.6.3.1).

The number and proportion of subjects with gynecomastia will be summarised by treatment regimen at each visit. A P-value for the comparison of the presence of gynecomastia between each dose of BGS649 and placebo will be provided using Fisher's exact test. A descriptive summary table for the size of glandular breast tissue will be presented for those subjects with gynecomastia.

Descriptive summary tables will be presented for all body composition bio impedance parameters [Total Fat (kg and percentage), Visceral adipose tissue, Total fat free mass (kg and percentage) and Skeletal muscle mass whole body, right arm, right leg, left arm, left leg and torso] values and change from baseline values by treatment regimen and visit.

The change from baseline in each parameter up to Week 24 will be analysed via MMRM in the same manner as the change from baseline in total testosterone (see Section 8.6.3.1).

A subgroup analysis of body composition parameters by baseline total testosterone (<200ng/dL vs ≥200ng/dL) as assessed by ICON central labs will be conducted. Descriptive summaries and analysis up to Week 24 as described above will be presented.

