8.7 Safety analyses

All definitions relative to safety endpoints are detailed in Section 7.1.4.

All safety analyses will be based on the Safety population and will be performed for all safety variables specified below.

No statistical tests will be performed.

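### The gynecomastia test against placebo ignores Screening status, so pre-existing cases dilute it; the descriptive liver table needs only a stated post-baseline window and a shift

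*SAP*

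**What the plan says.** **Gynecomastia.** SAP 8.6.4.2 summarises the number and proportion of men with gynecomastia by regimen at each visit, and adds: "A P-value for the comparison of the presence of gynecomastia between each dose of BGS649 and placebo will be provided". The method is Fisher's exact test. No baseline term, new-onset definition or shift table is given. The analysis is exploratory and uses the ITT population (SAP 8.6.4). Protocol 8.4 (objective 7) sets the aim as body composition change, with gynecomastia included. Protocol 12.2 lists change in physical examination, including breast, as a safety endpoint. The breast examination is scheduled at Screening, Week 12 and Week 24 (Protocol Table 9–1).

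Pre-existing cases can enter. Protocol Appendix II lists "Gynecomastia" among the signs suggestive of androgen deficiency that inclusion criterion 6 refers to, and nothing in Protocol 9.3.2 excludes it.

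**Liver.** SAP 8.7.2.3 says: "The number and proportion of subjects with laboratory values for liver function and enzymes of clinical concern as follows will be presented descriptively". The ALT and AST rows start at "> 1.5 times the upper limit of the normal range (ULN") and run to more than 10 times ULN. Bilirubin has rows above 2 and 3 times ULN, and there is a combined ALT/AST and bilirubin row. No visit window or baseline status is given. Protocol 9.3.2 excludes "Aspartate aminotransferase (AST) or alanine aminotransferase (ALT) > 3 times the ULN or bilirubin" at or above 2 times ULN at Screening, with bilirubin exempt from that limit "unless caused by Gilbert syndrome". SAP 8.7 opens its safety section with "No statistical tests will be performed".

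**The concern.** A test of presence answers a question about prevalence at a visit. The objective asks about change. A man with gynecomastia at Screening who still has it at Week 24 counts as a case in either arm and says nothing about the drug, yet he adds variance and shrinks the contrast between arms. New onset in some men and resolution in others can also offset each other in a prevalence figure.

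At stake is whether the trial can show a change in breast tissue with the power that its own data allow. The SAP already refers categories to baseline elsewhere: the bone density shift table (8.7.6), and the sperm concentration shift table and transitions (8.6.4.7).

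The liver table raises a smaller version of the same issue. A man eligible at, say, 2.5 times ULN could fall in the two lowest ALT or AST rows before his first dose if pre-dose values are not ruled out.

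**Working it through.** **Plan's own figure.** The documents give no power for either display. The 67 per dose group comes from the primary endpoint (SAP 5: goal 75%, true rate 90%, one-sided 2.5%). Exact binomial: 58 or more of 67 are needed, with alpha 1.60% and power 87.1%. The continuity-corrected normal approximation gives 85.5%. The stated 85% is thus slightly conservative, and 67 is used below.

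**Inputs.** n = 67 per arm; Fisher's exact test, two-sided 5% (SAP 8.1.4). Baseline prevalence b and new-onset rates q are not in the documents; they are assumed and varied. No dropout and, for the power figures, no resolution.

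**Step 1: the planned test.** Expected prevalence in an arm is b + (1 − b)q. At b = 20%, this is 0.20 + 0.80 × 0.15 = 0.320 on a dose and 0.20 + 0.80 × 0.03 = 0.224 on placebo. About 0.20 × 67 = 13 men per arm are cases before dosing.

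**Step 2: the stratified exact test.** Without resolution, every man in the stratum with gynecomastia at Screening is a case in both arms, so that stratum carries no information. The test reduces to Fisher's test among men free of it. The numbers free, i and j, are independent Binomial(67, 1 − b), so power = Σᵢ Σⱼ P(i) P(j) × Fisher power(i, j; 15%, 3%). The last column instead fixes equal numbers free in both arms, where Fisher's test is more conservative because of discreteness.

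| Baseline prevalence (assumed) | Expected prevalence, dose v placebo | Planned test | Stratified exact test | Men free at Screening, fixed equal arms |
|---|---|---|---|---|
| 0% | 15.0% v 3.0% | 59% | 59% | 59% (67 per arm) |
| 10% | 23.5% v 12.7% | 29% | 58% | 52% (60 per arm) |
| 20% | 32.0% v 22.4% | 19% | 52% | 45% (54 per arm) |
| 30% | 40.5% v 32.1% | 13% | 45% | 37% (47 per arm) |

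**Step 3: other assumed onset rates.** Planned test against Fisher's test in men free at baseline (fixed equal arms), at b = 10%, 20% and 30%:
- 15% v 2%: 35.0%, 21.6%, 15.2% against 64.0%, 56.5%, 46.5%.
- 20% v 5%: 40.8%, 26.8%, 18.6% against 62.7%, 55.8%, 46.8%.

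**Step 4: type I error.** With equal new onset of 5% in both arms, the planned test rejects in 1.3%, 2.9%, 3.2% and 3.4% of trials at b = 0%, 10%, 20% and 30%. The stratified test rejects in less than 2%. Both are below 5%.

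**Step 5: cancellation.** With resolution rate r, prevalence is b(1 − r) + (1 − b)q. At b = 20%, r = 40% and q = 10% (all assumed), this is 0.12 + 0.08 = 0.20, the starting value. Real movement in both directions would look like no change.

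**Step 6: liver, lowest rows only.** With assumed new onset of 10% v 3% the true ratio is 3.33. If men already above the threshold were counted, at b = 10% the table would show 0.10 + 0.90 × 0.10 = 0.190 against 0.10 + 0.90 × 0.03 = 0.127, a ratio of 1.50. At b = 5% and 20% the ratio would be 1.85 and 1.25.

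**The case against.** Several points on the other side stand.

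- **A false difference.** A reader might infer that pre-existing cases can manufacture a drug effect. A chance gap of 10 points or more at baseline between two arms of 67 has probability 6.1%, 16.0% and 22.0% at b = 10%, 20% and 30%. But randomisation makes that gap part of the test's error rate, which step 4 shows below 5%. SAP 8.6.4.2 summarises by visit, and SAP 8.1.3 presents each visit at which a parameter is scheduled. Screening prevalence by arm would therefore probably be visible.
- **Liver counts.** A reader might also infer that the liver table counts pre-dose abnormalities. The SAP does not say so; it is silent on the window. Table shells are in a separate document (SAP 1) and may settle it.
- **Liver exposure is narrow.** The entry limits largely protect the rows from 3 times ULN upward, the combined row, and bilirubin outside Gilbert syndrome. A rise between Screening and Day 1 is the main remaining route. With no test on this table, the power figures do not apply to it.
- **Other displays help.** For quantitative laboratory values, SAP 8.7.2.1 states: "Similarly, changes from baseline (and changes from screening for selected renal parameters; creatinine, urea, and glomerular filtration rate) will be summarised". Events that begin or worsen after the first dose are tabulated as TEAEs (SAP 7.1.4.1 and 8.7.1). These limit the risk of missing a liver or breast signal, but neither shows how many men newly crossed a threshold, or developed or lost gynecomastia.
- **Low stakes.** The test is exploratory, and Protocol 13.5.1 treats all analyses so.

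None of this answers the central point: the breast status needed to sharpen the test is already collected and is not used.

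**Conclusion.** The point holds for gynecomastia as a loss of power and a mismatch with the objective of change. At an assumed 20% baseline prevalence and new onset of 15% v 3%, power is about 19% as planned and roughly 52% with an exact test stratified on Screening status (45% if the numbers free of it are fixed and equal). The exact loss depends on prevalence and onset rates that the documents do not give. In every assumed case with pre-existing gynecomastia, the planned test had less power.

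The documents do not support the stronger reading that the planned test creates false differences, or that the liver table is known to count pre-dose cases. The liver item is a missing specification in a descriptive table, relevant mainly to ALT and AST above 1.5 and 2 times ULN and to bilirubin in Gilbert syndrome. Neither item affects the primary endpoint.

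**What to change.** **SAP 8.6.4.2.** Replace the unstratified Fisher test with an exact Cochran-Mantel-Haenszel test stratified on gynecomastia at Screening, each dose against placebo, and name the visits tested (Week 12 and Week 24). Report by arm the number with new onset among men without it at Screening, and the number with resolution among men with it. The separate counts are needed as well as the test, because a stratified test still nets opposite movements in the two strata.

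**SAP 8.7.2.3 (minor).** State that counts use post-baseline values. Add a shift from baseline category to worst post-baseline category for ALT, AST and bilirubin, with men who have Gilbert syndrome identified in the bilirubin rows.

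**Cost.** SAP wording and table shells, settled before unblinding, with a few extra table rows. No new data, visits or subjects.

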8.7.3 Vital signs

Vital sign assessments will be performed at each visit in the Randomisation Phase and Week 36.

Descriptive statistics (observed values and changes from baseline) will be presented for each treatment regimen and time-point for vital sign measurements (body temperature, pulse rate, systolic blood pressure, diastolic blood pressure, weight and BMI).

The change from baseline in systolic and diastolic blood pressure to Week 24 will also be analysed via MMRM in the same manner as the change from baseline in total testosterone (see Section 8.6.3.1).

Boxplots of observed and change from baseline values by treatment and visit will also be generated for both systolic and diastolic blood pressure.

In addition the number and percentage of subjects meeting each of the criteria below will be presented:

- Normal: SBP <120mm Hg and DBP < 80 mm Hg
- Elevated BP: 120≤SBP ≤ 129 mm Hg and DBP < 80 mmHg
- Hypertension Stage 1: 130≤SBP ≤ 139 mmHg or 80≤DBP ≤ 89 mmHg
- Hypertension Stage 2: SBP ≥ 140 mm Hg or DBP ≥ 90 mmHg

- SBP Change from baseline ≥20 mmHg
- DBP Change from baseline ≥10 mmHg

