12.6 Vital Signs

Vital signs include measurement of oral temperature, SBP, DBP, pulse and weight. Height will also be measured at Screening only, to enable BMI determination ([Section 11.3.2](#)).

Details on body weight measurement are provided in [Section 11.3.2](#). Body weight taken at Baseline will be utilised for all PK calculations.

Blood pressure (SBP and DBP, see [Section 11.3.2](#)) and pulse rate will be assessed after the subject has rested quietly in the supine position for at least 5 minutes. Three consecutive recordings will be taken and the average value will be noted in the eCRF. Blood pressure will be assessed using the same arm each time.

12.7 12-Lead ECG

The subject number and initials or date of birth, the date and actual time of the tracing, and the study code must appear on each page of the tracing. The ECGs should be performed at approximately the same time of day at each of the ECG assessments, after subject has been in supine position for 10 min. Tracings will be dated and signed by the person who interprets the ECG.

The CRFs will contain:

1. Date and time of the ECG
2. Heart rate
3. PR interval
4. QT interval (QT_CF)
5. QRS duration.
6. RR interval

The overall interpretation will be collected with a yes/no statement to confirm if any clinically significant abnormalities are present, which need to be detailed further and reported as AE/SAE if appropriate. Original ECG tracings, appropriately signed, will be archived at the study site.

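### The Stage 1 and Stage 2 blood-pressure criteria in SAP 8.7.3 overlap, so the Stage 1 row is inflated; unrounded averages could also fall in no category

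*SAP*

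**What the plan says.** After the descriptive statistics, the MMRM and the boxplots, SAP 8.7.3 (Vital signs) adds a categorical display: "In addition the number and percentage of subjects meeting each of the criteria below will be presented". Four of these criteria are blood-pressure grades:

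- The lowest grade, Normal, needs a systolic value under 120 together with a diastolic value under 80.
- The second grade, Elevated, needs a systolic value from 120 to 129 together with a diastolic value under 80.
- The third grade is worded "Hypertension Stage 1: 130≤SBP ≤ 139 mmHg or 80≤DBP ≤ 89 mmHg".
- The top grade, whose two conditions are likewise alternatives, is worded "Hypertension Stage 2: SBP ≥ 140 mm Hg or DBP ≥ 90 mmHg".

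Two change-from-baseline criteria follow, a rise of at least 20 mmHg in SBP and of at least 10 mmHg in DBP. The section gives no order of precedence among the four grades and plans no blood-pressure shift table.

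Protocol 12.6 (Vital Signs) describes the measurement: "Three consecutive recordings will be taken and the average value will be noted in the eCRF". Neither document states a rounding rule for that average.

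**The concern.** The four labels read as a graded classification. Normal and Elevated join their two conditions with *and*, so they exclude each other and both higher grades. Stage 1 and Stage 2 use *or*, and Stage 1 lacks a clause removing men who already qualify for Stage 2. Programmed as written, the Stage 1 row is not the number of men whose worst grade is Stage 1. A programmer who assumes a hierarchy would produce a different table from the same text.

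The upper limits 129, 139 and 89 are whole numbers, and the next limits are 130, 140 and 90. An average of three readings can lie between them.

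Change in vital signs is a listed safety endpoint (Protocol 12.2, SAP 4.4). A reader comparing arms would expect the Stage 1 row to mean Stage 1 and no higher.

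**Working it through.** The plan states no figure to reproduce, because the point concerns category logic. The criteria are applied to one reading per man per visit, in line with the by-time-point descriptive statistics in the same section.

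**Step 1. Whole-number values.** All pairs with SBP 80 to 220 and DBP 40 to 130 were checked: 141 × 91 = 12,831 pairs.

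- Pairs meeting no criterion: 0.
- Pairs meeting exactly one: 11,611.
- Pairs meeting two: 1,220, all of them Stage 1 with Stage 2.

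The overlap has two parts:

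- SBP ≥140 with DBP 80–89: 81 × 10 = 810 pairs.
- SBP 130–139 with DBP ≥90: 10 × 41 = 410 pairs.
- Total: 810 + 410 = 1,220.

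These counts show where the overlap lies, not how many men fall there.

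| Value | Criteria met |
|---|---|
| 135/85 | Stage 1 |
| 145/85 | Stage 1 and Stage 2 |
| 135/95 | Stage 1 and Stage 2 |
| 150/75 | Stage 2 |
| 150/95 | Stage 2 |

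A man who moves from 135/85 to 145/85 stays in the Stage 1 count and is added to Stage 2.

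**Step 2. Averages kept in thirds of a mmHg.** Values of 129.3/75, 139.7/75 and 115/89.3 meet no criterion. A value of 139.5/85 is still Stage 1, because its DBP qualifies. A gap therefore needs one component between limits and the other not qualifying for Stage 1 or Stage 2.

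**Step 3. Illustrative size.** The documents give no blood-pressure distribution. Assumption: bivariate normal, SD 14 (SBP) and 9 (DBP), values rounded to whole numbers except in the last column, where they are kept in thirds.

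| Mean SBP/DBP | Correlation | Stage 1 as written | Stage 1, highest grade only | Stage 2 | Stage 2 men also in Stage 1 | Sum of four rows | In no grade (thirds) |
|---|---|---|---|---|---|---|---|
| 125/78 | 0.5 | 45.9% | 35.9% | 20.7% | 48.6% | 110.0% | 1.8% |
| 125/78 | 0.7 | 43.9% | 33.8% | 19.1% | 53.1% | 110.1% | 1.5% |
| 130/82 | 0.5 | 54.8% | 38.2% | 34.9% | 47.6% | 116.6% | 1.8% |
| 130/82 | 0.7 | 52.6% | 37.2% | 32.0% | 48.2% | 115.4% | 1.5% |
| 135/85 | 0.5 | 56.8% | 34.5% | 49.4% | 45.2% | 122.3% | 1.6% |
| 135/85 | 0.7 | 54.5% | 34.6% | 46.0% | 43.3% | 119.9% | 1.3% |

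For whole numbers the excess over 100% equals the double-counted share. In the third row, 54.8 − 38.2 = 16.6 points, and the sum is 116.6%.

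**Step 4. Direction of the Stage 1 row.** Assume a shift of +5/+3 mmHg from 130/82 with correlation 0.6.

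- Stage 1 as written = Stage 1 only + both. Before: 37.67 + 16.17 = 53.84%. After: 34.50 + 21.32 = 55.82%.
- Stage 1 by highest grade falls from 37.67% to 34.50%.
- Stage 2 rises from 33.5% to 47.8% under either definition.

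The written Stage 1 row rises while the exclusive one falls. The Stage 2 row shows the whole deterioration.

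**The case against.** The strongest reply is that nothing is lost. The text promises "the number and percentage of subjects meeting each of the criteria below will be presented", not a partition, and the same list holds two change criteria that plainly overlap the grades. SAP 8.7.2.3 uses nested liver-enzyme thresholds in the same manner. For whole-number values, exclusive Stage 1 can be recovered as n minus Normal minus Elevated minus Stage 2. Table templates are in a separate document that might state a hierarchy. Blood pressure is also covered elsewhere in the section: "The change from baseline in systolic and diastolic blood pressure to Week 24 will also be analysed via MMRM", and there are boxplots and the 20 and 10 mmHg change criteria. SAP 8.7 plans no tests on safety data in general, and none is specified for these grades.

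Most of this stands and limits the consequence. It does not remove the defect. Nested enzyme thresholds are visibly cumulative. Here three of the four rows mean what their labels suggest and one does not, and a reader should not have to recover the fourth by subtraction.

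Two stronger readings are not supported. A reader might infer that the table hides progression from Stage 1 to Stage 2. It does not, because every man at SBP ≥140 or DBP ≥90 is in the Stage 2 row. Individual transitions are not shown, but that is because no shift table is planned. A reader might also infer that every Stage 2 man is counted twice, or that the grades certainly leave gaps. Values such as 150/95 and 150/75 are counted once, and gaps need decimal averages, which the protocol allows but does not establish.

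**Conclusion.** The point holds, as a minor one. That Stage 1 and Stage 2 overlap follows from the SAP wording without any assumption. The effects are an inflated Stage 1 row, four percentages that can exceed 100% in total, and a Stage 1 count that need not fall as men progress.

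The size is illustrative only. Under the assumed distributions, 43 to 53% of Stage 2 men are double-counted and Stage 1 reads 44 to 57% instead of 34 to 38%. Those assumptions were not calibrated to this trial, which excludes recent uncontrolled hypertension, so the true overlap could be smaller. The gap affects about 1 to 2% of men under the same assumptions, and only if averages keep their decimals.

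The impact is confined to one descriptive safety display. The primary endpoint, the MMRM and the Stage 2 count are unaffected.

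**What to change.** In SAP 8.7.3, assign each subject-visit to the highest grade met and use continuous limits:

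- Stage 2: unchanged.
- Stage 1: not Stage 2, and SBP ≥130 or DBP ≥80. The ranges are then 130≤SBP<140 and 80≤DBP<90.
- Elevated: 120≤SBP<130 and DBP <80.
- Normal: unchanged.

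Every pair, whole or fractional, then falls in exactly one grade; this was checked on 114,091 pairs in thirds of a mmHg. Leave the two change-from-baseline criteria as they are. If individual transitions are of interest, a baseline-to-visit shift table would show them.

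The cost is a wording change and one derivation. No new data are needed.
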